# 6.8.2 Procedures for Premature Termination or Suspension of the Study or the Participation of Investigational Site(s)

In the event that the Sponsor, an institutional review board (IRB)/independent ethics committee (IEC), or regulatory authority elects to terminate or suspend the study, study-specific procedures for early termination or suspension will be provided by the sponsor; the procedure will be followed by ICON during the course of termination or study suspension.

#### 6.9 Study Plan

Table 6: Data collection overview

	Time point #1: Patient Survey Completion	Time point #1: Caregiver of a Pediatric Patient Survey Completion	Time point #1: Caregiver of an Adult Patient Survey Completion
Informed consent	X	X	x
Web-based screening (Inclusion/exclusion criteria)	x	X	x
HAE Patient Survey	Х		
Caregiver of a Pediatric Patient Survey		X	
Caregiver of an Adult Patient Survey			Х
Angioedema Control Test (AECT)	х		
Angioedema Quality of Life Questionnaire (AE-QoL)	x		
Work Productivity and Activity Impairment	X		

Questionnaire: General Health v2.0 (WPAI:GH)		
12-Item Short Form (SF-12 v2.0)	X	
Hospital Anxiety and Depression Scale (HADS)	Х	

#### 7 Safety Reporting

#### 7.1 Definitions

#### **Adverse Event**

An adverse event (AE) is any untoward medical occurrence in a participant administered a medicinal product and which does not necessarily have to have a causal relationship with this treatment. An AE can therefore be any unfavorable and unintended sign (including an abnormal laboratory finding), symptom, a new disease or worsening in severity or frequency of a concomitant disease, temporally associated with the use of a medicinal product, whether or not the event is considered causally related to the use of the product.

Although abnormal laboratory values are typically not considered AEs, the following considerations may result in an abnormal laboratory value being considered an AE:

- A laboratory test result that meets the criteria for an SAE
- A laboratory test result that requires the participant/patient to receive specific corrective therapy
- A laboratory abnormality that leads to discontinuation of therapy
- A laboratory abnormality that the health care provider considers to be clinically significant

#### **Serious Adverse Events**

A Serious Adverse Event (SAE) is any untoward medical occurrence that at any dose:

- Results in death. Note that death is an outcome of an event. The event(s) causing death should be recorded.
- In the view of the Health care provider, places the participant/patient at immediate risk of death (a life threatening event); however, this does not include an event that, had it occurred in a more severe form, might have caused death
- Requires inpatient hospitalization or prolongation of existing hospitalization
- Results in persistent or significant disability/incapacity
- Results in a congenital anomaly/birth defect

An SAE may also be any other medically important event that, in the opinion of the Health
care provider, may jeopardize the participant/patient or may require intervention to
prevent one of the other outcomes listed in the definition above. (Examples of such
medical events include allergic bronchospasm requiring intensive treatment in an
emergency room or convulsions occurring at home that do not require an inpatient
hospitalization.)

# **Adverse Drug Reactions**

An adverse drug reaction (ADR) is an AE for which there is at least a reasonable suspicion of a causal relationship between an AE and a suspected medicinal product.

#### **Product Quality Issues**

A Product Quality Issue (PQI) refers to defects related to the safety, identity, strength, quality, or purity of the product or with the physical characteristics, packaging, labeling, or design of the product.

# **Special Situation Reports**

A Special Situation Report (SSR) includes any of the following events:

- Pregnancy: Any case in which a pregnancy patient is exposed to a Takeda Product or in
  which a female patient or female partner of a male patient becomes pregnant following
  treatment with Takeda Product. Exposure is considered either through maternal exposure
  or via semen following paternal exposure.
- Breastfeeding: Infant exposure from breast milk
- Overdose: All information of any accidental or intentional overdose
- Drug abuse, misuse or medication error: All information on medicinal product abuse, misuse or medication error (potential or actual)
- Suspected transmission of an infectious agent: All information on a suspected (in the sense of confirmed or potential) transmission of an infectious agent by a medicinal product.
- Lack of efficacy of Takeda Product
- Occupational exposure

- Use outside the terms of the marketing authorization, also known as "off-label"
- Use of falsified medicinal product

A SSR should be reported even if there is no associated AE.

#### Relationship of an AE to studied drug(s)

- Related (Yes): An AE that follows a reasonable temporal sequence from administration of the medication, vaccine or device (including the course after withdrawal of the medication), or for which a casual relationship is at least a reasonable possibility, i.e., the relationship cannot be ruled out, although factors other than the medication, vaccine or device, such as underlying diseases, complications, concomitant drugs and concurrent treatments, may also be responsible.
- Not related (No): An AE that does not follow a reasonable temporal sequence from administration of the medication, vaccine or device and/or that can reasonably be explained by other factors, such as underlying disease, complications, concomitant drugs and concurrent treatments. The investigator must make an assessment of causality using the above definition. Causality cannot be assumed in the absence of the investigator's assessment.:

# 7.2 Collection and notifying of Adverse Events, Special Situation Reports and Product Quality Issues to Takeda Pharmacovigilance

# SAEs, AEs, ADRs, SSRs and PQIs in the medical record/source data that are part of the study objectives or endpoints

Events/issues which are part of the study objectives or endpoints will be systematically identified and collected from medical records or other applicable source records, and summarized as part of any interim analysis and in the final study report. Such events do not need to be notified as individual reports to Takeda Pharmacovigilance.

SAEs, AEs, SSRs and PQIs in the medical records/other applicable source data that are not part of the study objectives and endpoints

Events/Issues which are not part of the study objectives and endpoints will not be abstracted or collected from medical records/ source records.

#### 8 Data Quality Control and Assurance

# 8.1 Quality Control

ICON will assure database quality by reviewing the data for missing values and accuracy. All data will be anonymized and kept confidential.

ICON maintains a high quality of work through a stringent quality control process that includes full internal quality control checks and will include:

- Review of study procedures and all methods detailed in the protocol.
- Confirmation that the source of the data and/or results has been documented and that results and data have been verified against the source.
- Checking the internal consistency of any research data presented in the document.
- Confirmation that the conclusions are accurate, objective, balanced, and consistent with other published or released results.
- Confirmation that the format and content of the document are aligned with applicable Shire requirements.
- Final annotated version of any disclosures (abstracts, posters and manuscripts).

#### 8.2 Audit from Quality Assurance Unit

The Quality Assurance (QA) unit may audit the study to ensure that study procedures comply with the protocol and standard operating procedures, and that collected data is correct and complete.

#### 8.3 Inspection by IRB/IEC or Competent Authority

Representatives from IRBs/IECs may in rare cases wish to inspect the study. Upon receiving notification of such inspection, ICON must immediately contact Global Research and must make the records available as requested. The Inspector must be reminded up front that consent electronic consent has been obtained from the participants in this study.

#### 8.4 Data Management

[figure not shown]
The survey will be hosted on secure SSL servers. Data files will be password protected and transferred using an encrypted system. ICON will maintain study records for 20 years per Takeda's master service agreement, or longer as required by local laws or regulations for participating country sites, following conclusion of the study and will notify the sponsor prior to the destruction of study records. ICON will give Takeda (or designee) access to all relevant source documents to confirm their consistency. Informed consent will be electronic and included in the survey database. In all cases, patient identifiers will not be collected or transmitted to the study sponsor.

#### 8.4.1 Data Collection Tools and Flow

The Study Site will receive data collection tools access to electronic data capture etc.) from ICON.

Figure 1 provides a diagrammatic representation of the study design and data collection flow.

Figure 1

# 9 Statistical Methods and Determination of Sample Size

This section describes the statistical analyses as foreseen at the time of planning the study. Any known deviations from the planned analyses, the reason for such deviations and all alternative / additional statistical analyses that may be performed as well as the final statistical analysis must be described in a revised Statistical Analysis Plan (SAP) before completion of data collection. All later deviations and / or alterations will be summarised in the Study Report.

#### 9.1 Statistical Analysis Plan

#### 9.1.1 HAE Patient Survey

For each of the primary objectives of the HAE Patient Survey, data will be analyzed based on the total sample and each subgroup:

- Country
- HAE Type (Type I, II, normal functioning C1-INH, and unknown)
- By long-term prophylactic treatment status (LTP) (Currently on a long-term prophylactic treatment vs. not currently on a long-term prophylactic treatment)
  - o Among those on LTP, comparison by number of angioedema attacks in the past 6 months (0 attacks, 1-3 attacks, 4-6 attacks, 7-12 attacks, ≥13 attacks)
  - Among those on LTP, comparison of C1-INH, Androgens, and Tranexamic Acid
  - Among those on C1-INH LTP, comparison by number of attacks in the past 6 months
  - Among those on Androgen LTP, comparison by number of attacks in the past
     6 months
- On-Demand Treatment Status (Currently using on-demand treatment vs. no on-demand treatment)
  - Among those on on-demand treatment, comparison by number of angioedema attacks in the past 6 months (0 attacks, 1-3 attacks, 4-6 attacks, 7-12 attacks, >13 attacks)
- HADS subscale scores for anxiety and depression (for each subscale, including normal, mild, moderate, and severe)
- AECT Control Category (Controlled vs. Uncontrolled)

Objective 1: To describe patient characteristics, including demographics and clinical characteristics overall and separately for each subgroup.

Appropriate descriptive summary statistics (e.g. mean and SD, median and interquartile range) will be presented for patient characteristics overall and for each subgroup. Demographic characteristics will include age, sex, education level, marital status, insurance type, residence, and employment status. Clinical characteristics will include HAE type, age at onset and diagnosis, family history; frequency of attacks; and severity, duration, and location of the most recent angioedema attack.

Objective 2: To describe the patient perspective on the humanistic burden of HAE including: **a**) disease control (AECT), **b**) health-related quality of life scores (SF-12 and AE-QoL), and **c**) psychosocial well-being scores (HADS) overall and for each subgroup listed below.

• Appropriate descriptive statistics will be used to summarize PRO scores on measures associated with patients' perspectives on the humanistic burden of HAE. The data will be presented overall and within each subgroup as relevant. For health-related quality of life, SF-12 domain and component scores as well as AE-QoL dimension and total scores will be described. HADS subscale scores will be summarized as indicators of psychosocial well-being.

Objective 3: To describe the economic burden associated with HAE as experienced by patients including the direct costs of illness, work productivity and absenteeism (WPAI-GH), treatment history, and health-care resource utilization overall and for each subgroup.

 Appropriate descriptive statistics will be presented for survey items and PRO scores related to costs of illness, impacts on work, history of treatment, and health-care resource utilization. The data will be provided overall as well as within each subgroup.

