# 2 Introduction

Hereditary angioedema (HAE) is a rare genetic disorder characterized by recurrent episodes of edema in the face, extremities, trunk, abdomen, genitals, and upper respiratory tract (Bygum et al., 2012; Betschel et al., 2014). Angioedema attacks can be random or occur as the result of trauma. The frequency and duration of attacks can vary. Untreated patients experience attacks every one to two weeks on average, with most episodes lasting three to four days (Bygum et al., 2012, Genetics Home Reference, 2017). HAE is estimated to affect 1 in every 50,000 in the general population (Bygum et al., 2012). Symptoms usually begin in childhood and worsen during puberty; however, 6.1-13.7% of patients may be asymptomatic or have delayed symptom onset (Bygum et al., 2012). The rarity and lack of awareness of the condition often result in delayed diagnosis (Bygum et al., 2012).

HAE is caused by C1 inhibitor deficiency and is categorized into three types depending on the level and function of the C1 inhibitor. HAE Type I is the most common form, representing approximately 85% of cases, and is caused by low antigenic and functional levels of C1 inhibitor. HAE Type II accounts for approximately the remaining 15% of cases and is associated with a normal C1 inhibitor protein level, but impaired function of the protein. The third type of HAE is associated with normal C1 inhibitor function (HAE-nC10INH) and is rare; it's true prevalence and exact pathogenesis are unknown (Betschel et al., 2014; Genetics Home Reference, 2017).

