# **6.4** Definitions of Study Variables

# 6.4.1 Outcome/Endpoint Variables

#### **6.4.1.1** Patient Survey

The patient survey includes items in the following content areas:

- Demographic characteristics (e.g., age, sex, education level, marital status, insurance type (if applicable), residence, employment status)
- Clinical and disease characteristics (e.g., HAE type, age at onset and diagnosis, family history, HAE symptoms; frequency of attacks; and duration, severity, and location of the most recent angioedema attack).
- Individual economic burden of illness including direct costs of illness, work productivity and absenteeism, treatment history, and health-care resource utilization.
- Information on humanistic burden of illness, including health-related quality of life.

Table 3. HAE Patient survey variables to be used in the analyses

Variable	Туре
Subject ID	Continuous variable
Country	Categorical variable
Age	Continuous variable
Gender	Dichotomous variable
Race	Categorical variable
Marital status	Categorical variable
Insurance type	Categorical variable
Residence	Categorical variable
Education	Ordinal variable
Employment status	Categorical variable
Type of health insurance	Categorical variable
Household income	Ordinal variable
HAE type	Categorical variable
Age at onset (years)	Continuous variable
Age at diagnosis (years)	Continuous variable
Number of doctors seen	Continuous variable
Family History	Categorical variable
Family History of Suffocation	Categorical
Frequency of attacks	Continuous variable
Duration of most recent attack	Ordinal variable

Severity of most recent attack	Ordinal variable
Location of most recent attack	Categorical variable
Current long-term prophylactic use	Dichotomous variable
Duration of long-term prophylactic treatment	Ordinal variable
Current long-term prophylactic treatment	Categorical variable
Frequency of long-term prophylactic treatment	Ordinal variable
Current short-term prophylactic use	Dichotomous variable
Current short-term prophylactic treatment	Categorical variable
Past long-term prophylactic use	Dichotomous variable
Past long-term prophylactic treatment	Categorical variable
Reasons for discontinuing past long-term prophylactic	Categorical variable
Past short-term prophylactic use	Dichotomous variable
On-demand treatment history	Categorical variable
HAE disease control	Ordinal variable
Treatment control	Categorical variable
Treatment satisfaction	Ordinal variable
Treatment convenience	Ordinal variable

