#### 9.1.5 Sensitivity Analyses

Not applicable.

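### Section 9.1.1 groups patients by current LTP use but counts attacks over the past 6 months, so for recent starters attacks from before LTP are tabulated as attacks on LTP

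*Protocol*

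**What the plan says.** Protocol section 9.1.1 defines the LTP subgroup by status at the time of the survey: "Currently on a long-term prophylactic treatment vs. not currently on a long-term prophylactic treatment". Within LTP users it plans "Among those on LTP, comparison by number of angioedema attacks in the past 6 months", in five categories from 0 to 13 or more. It repeats this by product class, for example "Among those on C1-INH LTP, comparison by number of attacks in the past 6 months", and likewise for androgens. It also plans "Among those on LTP, comparison of C1-INH, Androgens, and Tranexamic Acid".

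Attack frequency is a reported result as well as a stratifier. Under Objective 1, "Clinical characteristics will include HAE type, age at onset and diagnosis, family history; frequency of attacks" are summarised overall and for each subgroup, which includes LTP status and LTP type.

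Table 3 (section 6.4.1.1) lists "Duration of long-term prophylactic treatment" as an ordinal variable. Neither the objectives (3.1.1), the eligibility criteria (6.2.4.1, 6.2.5) nor section 9.1.1 sets a minimum time on LTP or ties the 6-month window to the LTP start. Section 9.1.5 on sensitivity analyses reads "Not applicable", and section 9.4 names only selection and recall bias.

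**The concern.** Exposure is measured at one moment and the attack count over the preceding 6 months. A patient one month into LTP is tabulated as an LTP user with a count of which five of the six months predate LTP. A table headed as attacks among LTP users then mixes two things: attacks that occurred on LTP, and attacks that may have been the reason for starting it.

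Two sets of results are exposed. Mean or categorised attack frequency in LTP users is too high if attacks are fewer on LTP, so the contrast with non-users is diluted. The comparison of C1-INH, androgens and tranexamic acid is disturbed unequally if the classes differ in their share of recent starters, and the direction depends on which class has more of them. Within LTP users, the strata with high counts also collect recent starters, whose AE-QoL (4-week recall) and SF-12 (1-week recall) may already describe life on LTP.

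**Working it through.** The protocol gives no figure to reproduce, so the check has two parts: whether the text aligns the two time frames, and how large the effect could be.

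**Text.** Section 9.1.1 uses current LTP status and a fixed 6-month look-back. No section requires LTP to have covered that look-back. The mismatch therefore follows from applying the plan as written to anyone who started within 6 months.

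**Inputs for the illustration**
- Attack rate off LTP: section 2 states "Untreated patients experience attacks every one to two weeks on average". Over 26 weeks that is 26/2 = 13 to 26/1 = 26 attacks.
- Ratio r of the attack rate on LTP to that off LTP: assumed, 0.5, 0.2 or 0.1.
- Share f of LTP users who started within 6 months: assumed, 5% to 30%, with start dates uniform over the window.
- Recent starters are taken to have been at the off-LTP rate before starting.

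**One patient, m months on LTP.** Expected count = off × (6 − m)/6 + on × m/6. With off = 13 and r = 0.2, on = 2.6:

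| Months on LTP | Expected count | Share from before LTP |
|---|---|---|
| 1 | 10.83 + 0.43 = 11.27 | 96% |
| 3 | 6.5 + 1.3 = 7.8 | 83% |
| 5 | 2.17 + 2.17 = 4.33 | 50% |
| 6 or more | 2.6 | 0% |

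At 3 months the expected count is 7.8 against a true on-LTP value of 2.6. If counts are Poisson, the chance of falling in the 7-12 category is 61% at a mean of 7.8 and 2% at a mean of 2.6. At 3 months the pre-LTP share is 67% for r = 0.5 and 91% for r = 0.1.

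**LTP group mean.** Recent starters average (off + on)/2, so the mean is on × (1 − f) + f × (off + on)/2. The relative inflation is f × (1/r − 1)/2, which does not depend on the off-LTP rate.

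| r | f = 5% | f = 10% | f = 20% | f = 30% |
|---|---|---|---|---|
| 0.5 | 2.5% | 5% | 10% | 15% |
| 0.2 | 10% | 20% | 40% | 60% |
| 0.1 | 22.5% | 45% | 90% | 135% |

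For example, with r = 0.2, off = 13 and f = 10%, the mean is 2.6 × 0.9 + 0.1 × 7.8 = 3.12 instead of 2.6. If non-users stay at the off-LTP rate, the apparent LTP/no-LTP ratio moves from 0.20 to between 0.22 (f = 5%) and 0.32 (f = 30%).

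**Two LTP types with the same true effect.** With r = 0.2 and off = 13, a type with 5% recent starters shows 2.86 attacks and a type with 30% shows 4.16. The ratio is 4.16/2.86 = 1.45, with no true difference.

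**With the split.** Among patients on LTP for at least 6 months the pre-LTP share is zero, and the mean equals the on-LTP rate.

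**The case against.** The strongest reply is that this is a descriptive survey. It states no treatment-effect estimand, it measures control directly with the AECT, and restricting a table by duration is ordinary SAP detail. The opening of section 9 allows additional analyses in a revised SAP before data collection ends, so the entry in 9.1.5 does not rule the split out. LTP duration is in the list of variables for analysis and could be tabulated by LTP type as treatment history under Objective 3, which would let readers see an imbalance in recent starters. All of this is fair and limits the weight of the point. It does not remove it: section 9.1.1 itself fixes the LTP-by-attack-count tables, and a table labelled as attacks among LTP users should describe attacks on LTP.

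A reader might infer more than the protocol supports:
- **That all LTP comparisons are biased.** The Secondary Objective 2 models in 9.1.4 use LTP use and type to explain AE-QoL, SF-12, WPAI-GH and direct cost, and do not name the attack count. The 6-month window does not distort those comparisons. Secondary Objective 1 uses the attack count but names no LTP term.
- **That the pediatric survey has the same fault.** Section 9.1.2 lists LTP status and attack count as separate subgroups, does not cross them, and does not name attack frequency among the clinical characteristics.
- **That the bias is known to be large.** The share of recent starters and the rate ratio are assumptions. Patients who switched from another LTP would have had fewer attacks before the switch than the untreated rate implies.
- **That the survey cannot support the fix.** The questionnaire is not shown. It may already have a 6-month break in the duration item and a stop date.

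**Conclusion.** The point holds for the patient-survey results in 9.1.1 that use the 6-month attack count: attack frequency by LTP status and LTP type under Objective 1, and the attack-count strata within LTP, C1-INH LTP and androgen LTP users. In these, attacks from before LTP are counted as on LTP for anyone who started the current LTP less than 6 months ago.

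The definitional mismatch is certain from the text; its size is not. At an assumed rate ratio of 0.2 with evenly spread start dates, 5% to 30% recent starters inflate the LTP mean count by 10% to 60%. Across ratios of 0.5 to 0.1 the range at 10% recent starters is 5% to 45%. With no recent starters it is zero. For LTP status the expected direction is dilution, provided attacks are fewer on LTP; for LTP type the direction cannot be foretold.

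The mirror problem exists too. Patients who stopped LTP within 6 months bring on-LTP attacks into the group not currently on LTP, and Table 3 lists past LTP use only as yes/no, with no stop date.

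**What to change.** In section 9.1.1, or in the SAP that implements it:
- Present every attack-count result for LTP users and LTP types in two rows: at least 6 months, and less than 6 months, on the current LTP. Use the duration variable in Table 3.
- Base any statement about attacks on LTP, or about differences between LTP types in attacks, on the first row.
- Confirm that the ordinal duration item has a break at 6 months and refers to the current LTP; neither its categories nor its wording are shown. If the nearest break is later than 6 months, cutting there still ensures full coverage of the window.
- State as a limitation that recent stoppers carry on-LTP attacks into the group not currently on LTP, unless the survey already records when LTP stopped.

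Leave the Secondary Objective 2 models as they are.

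If the break exists, the cost is wording and smaller cells. Country targets go down to 10 and section 9.3 already calls a sample of 20 hard to interpret, so the split is best shown for the pooled sample. If a category has to be changed before fielding, the survey needs updating in 11 languages, with ethics notification or approval as locally required.
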